## ***4.2. Adverse Events***

### **4.2.1. ADVERSE EVENT DEFINITIONS**

[figure not shown]
[figure not shown]
Adverse events (AE), serious adverse events (SAE), adverse device effects (ADE), [REDACTED]

[REDACTED] are defined as set forth in Section 12.1. of the protocol.

### **4.2.2. ADVERSE EVENT ANALYSIS**

Adverse events will be coded with MedDRA Preferred Term codes. Descriptive statistics (number and percent of eyes) will be presented for each MedDRA Preferred Term category of ocular adverse events and serious ocular adverse events reported, separately for first

implanted eye, second implanted eye and both eyes combined. Separate tables will be generated for AEs, SAEs, and ADEs. Descriptive statistics (number and percent of subjects) will be presented for each MedDRA Preferred Term category and System Organ Class of non-ocular adverse events and serious non-ocular adverse events reported. In addition, a one-sided upper 95% confidence interval on the percent of each MedDRA Preferred Term code will be calculated

A listing of all adverse events and serious adverse events including investigator, subject number, onset day, eye, lens model, causality assessment, severity, outcome and the MedDRA Preferred Term code for the adverse event will also be provided.

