## **8. STUDY DESIGN**

### ***8.1. Study Design***

Subjects enrolled in this study will attend postoperative visits for up to 10 years following the date of implantation and will be able to enroll at any time for the duration of this trial. These subjects will be followed postoperatively to Year 10/10A (3619 – 3740 days) at appropriate intervals as defined in Section 9.1.

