## 9. STUDY PROCEDURE

### 9.1. Study Visits and Examination

An Entrance Visit will be completed upon a subject's enrollment. Subjects may enroll in the study at any time, thus the Entrance Visit may coincide with any visit (Year 4/4A to Year 10/10A ).

Postoperative visits for the first and second implants may be performed simultaneously if both visits fall within the proper timeframes specified for each eye.

Subjects examined subsequent to Day 3740 and prior to study exit (eg, a planned visit occurring after the last study plan visit) will be included in the Year 10/10A analysis if:

a) no Year 10 or 10A Form was received previously, or
b) the original Year 10 or 10A exam was early, or
c) the subject was previously unavailable for the visit or previously discontinued.

Each required examination must be recorded on the corresponding electronic Case Report Forms (eCRFs) in a timely manner.

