#### 10.4.1.2. ADVERSE EVENTS

Descriptive statistics (number and percent of eyes) will be presented for each MedDRA Preferred Term category of ocular adverse events and serious ocular adverse events reported, separately for first implanted eye, second implanted eye, and for both implanted eyes combined. Descriptive statistics (number and percent of subjects) will be presented for each MedDRA Preferred Term category of non-ocular adverse events and serious non-ocular adverse events reported. A listing of all adverse events and serious adverse events reported during the study will also be provided.

[figure not shown]

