### **12.2. Procedures for Recording and Reporting**

All adverse events will be documented on the Adverse Event electronic case report form (eCRF) within the Electronic Data Capture (EDC) system and collected on a routine basis at monitoring visits. Adverse events must be collected from the time of informed consent.

In addition, the investigator must document all ADEs, SAEs, [REDACTED] with details including the date of occurrence, severity, treatment (if applicable), outcome, and assessments of the seriousness and causality. The site must submit all available information to the study sponsor immediately as follows:

- **ADEs or SAEs are documented on the *Adverse Device Effect and Serious Adverse Event Form* in the EDC system within 24 hours of the investigator's or site's awareness.**
- [REDACTED]  
[REDACTED]  
[REDACTED]
- **Additional relevant information after initial reporting is to be updated in the EDC system as soon as the data becomes available.**
- **Document any changes to the medical history and concomitant medication on the appropriate forms in the EDC system.**
- **All relevant documentation such as Discharge Summary, Autopsy Report, Certificate of Death etc, should be faxed to the study sponsor at [REDACTED].**

*Note:* Should the EDC system become non-operational, the site must complete the appropriate paper *Adverse Device Effect and Serious Adverse Event Form* [REDACTED]

[REDACTED] The completed form is faxed to the study sponsor at [REDACTED] within 24 hours of the investigator's or site's awareness; however, the reported information must be entered into the EDC system once it becomes available.

Study sponsor contact information is provided in Table 12.2.-1.

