***12.4. Follow-Up of Safety Information***

The investigator is responsible for adequate and safe medical care of subjects during the study and for ensuring that appropriate medical care and relevant follow-up procedures are maintained after the study. The investigator should provide the sponsor with any new safety information (which includes new adverse events and changes to previously reported adverse events) that may affect the safety evaluation of the device. Any additional data from these follow-up procedures performed up to 6 months after subject exit must be documented and available upon the study sponsor's request.

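### Adverse event percents and their upper limits are planned without any time at risk, although exposure per eye differs by design and includes time after explantation

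*SAP*

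**What the plan says.** **Summary measures.** SAP 4.2.2 states: "Descriptive statistics (number and percent of eyes) will be presented for each MedDRA Preferred Term category of ocular adverse events". These tables are split into first eye, second eye and both eyes combined, with separate tables for AEs, SAEs and ADEs. Protocol 10.4.1.2 has the same ocular summary, and for other events: "Descriptive statistics (number and percent of subjects) will be presented for each MedDRA Preferred Term category of non-ocular adverse events". The SAP then adds that "a one-sided upper 95% confidence interval on the percent of each MedDRA Preferred Term code will be calculated". A listing gives onset day, eye and lens model for each event. Nothing readable in either document plans total follow-up time, a rate per eye-year or a time-to-event estimate for adverse events.

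**Start of observation.** Protocol 12.2: "Adverse events must be collected from the time of informed consent". Protocol 8.1 says that subjects "will be able to enroll at any time for the duration of this trial", and Protocol 9.1 that "Subjects may enroll in the study at any time, thus the Entrance Visit may coincide with any visit", giving the range as Year 4/4A to Year 10/10A.

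**End of observation.** Protocol 8.1 plans follow-up to Year 10/10A (Days 3619 to 3740), and an Exit Form exists (Protocol 9.5 and 9.6). Neither document says in so many words when an event stops counting for the tables.

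**Explanted eyes.** Subjects explanted before entry are eligible (Protocol 7.1 and 7.2), and those explanted during the study stay in (Protocol 8.1.1 and 9.6). SAP 3.1.1 treats all collected data as evaluable with one exception, post-explantation cell density. That exception does not reach adverse events.

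**The concern.** A percent of eyes with an event grows with the time for which the eyes are watched. When that time is similar for everyone and is stated, the percent can be read as a risk over that period. Here one eye may be observed for more than six years and another for little more than a single visit, and both count as one in the denominator. An eye explanted before entry and not given another L-series lens also counts as one, although it contributes no lens-in-place time in this study.

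Adverse events are one of the two primary safety variables. The other, cell density loss, is annualised and has its post-explantation values removed from the main analyses. The adverse event summary has neither feature. Protocol 10.7 plans no formal test, so the estimates and their limits are themselves the safety result, and an upper limit without a time base can be taken as a ceiling on risk over a period that nobody has stated.

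**Working it through.** **1. The plan's own figure.** The Protocol summary and SAP section 1 give follow-up of 5 to 7 years. The windows in Protocol 8.1 and Table 17.-1 are Year 4, Days 1429–1550; Year 5, Days 1794–1915; Year 5.5 opens Day 1976; Year 10, Days 3619–3740. With 365.25 days per year:

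- Entry at Year 4: longest 3740 − 1429 = 2311 days = 6.33 years; shortest 3619 − 1550 = 2069 days = 5.66 years.
- Entry at Year 5: 3740 − 1794 = 1946 days = 5.33 years, down to 3619 − 1915 = 1704 days = 4.67 years.
- Entry at Year 5.5 or later: at most 3740 − 1976 = 1764 days = 4.83 years.
- Entry at Year 10: about 0.

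So 5 to 7 years does not follow from the schedule. Seven years is 2557 days, which is 246 more than the windows allow one eye. A subject could reach it if the second eye was implanted at least 246 days after the first, or under the Protocol 9.1 rule for "Subjects examined subsequent to Day 3740 and prior to study exit".

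Footnote d of Table 17.-1 says that all patients are already past Year 4.5. An eye first entering at Year 5 has at most about 5.3 years, so the 6.3-year maximum applies only to eyes that entered at Year 4.

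**2. Effect on the percent.** The documents give no event rates and no entry distribution, so everything here is assumed: 1321 eyes (the planned maximum), a constant hazard h = 0.01 per eye-year, and follow-up to Year 10.

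- Percent = average over entry times of 1 − exp(−hT), where T = 10 − entry year.
- Limit = exact one-sided 95% binomial, treating eyes as independent.

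| Entry pattern | Mean years | Eye-years | Eyes with event | Percent | Upper limit |
|---|---|---|---|---|---|
| All at Year 5 | 5.00 | 6605 | 64 | 4.9% | 5.93% |
| Half at Year 5, rest even over the six visits 5.5–8 | 4.12 | 5449 | 53 | 4.0% | 5.02% |
| Even over the eleven visits 5–10 | 2.50 | 3302 | 32 | 2.5% | 3.24% |

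Events over total eye-years are 64/6605, 53/5449 and 32/3302, or 0.97 per 100 in each row. Counting time only to the first event gives 1.0, the assumed hazard. The percent moves while the rate does not.

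**3. Sensitivity**, in the same row order.

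- At 0.5 per 100: 2.5, 2.0 and 1.2%. At 3 per 100: 13.9, 11.6 and 7.1%.
- If 20% leave evenly between entry and Year 10 (at 1 per 100): 4.4, 3.6 and 2.2%.
- Hazard rising from 0.5 to 1.5 per 100 over Years 4–10: percents 5.3, 4.6 and 3.0; rates to first event 1.08, 1.13 and 1.21. Falling from 1.5 to 0.5: percents 4.5, 3.5 and 2.0; rates 0.92, 0.87 and 0.79. A single rate then also depends on the entry mix, but much less.

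**4. Off-lens eyes.** If 5% or 10% of eyes have no lens throughout and cannot have a device event, 4.9% becomes 4.9 × 0.95 = 4.6% or 4.9 × 0.90 = 4.4%.

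**5. Two eyes per subject.** If the maximum of 778 subjects supplies 1321 eyes, then 1321 − 778 = 543 are bilateral and 235 unilateral. The design effect is 1 + ρ[(543 × 4 + 235)/1321 − 1]. At an assumed ρ = 0.5 it is 1.41, the effective number of eyes is 936, and the limits rise to 6.2, 5.3 and 3.5%.

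**6. No events.** The limit is 1 − 0.05^(1/1321) = 0.23%, whether those eyes were followed for six months or six years.

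**The case against.** The plan offers more than a bare percent. It separates AEs, SAEs and ADEs, an ADE is device-related by definition, and the listing gives onset day and eye. That stands, but none of it supplies time at risk for eyes without an event.

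A reader might infer from the table that the reported percents will be wrong by a factor of two. The documents do not support that. The two-fold contrast needs entry spread evenly over Years 5 to 10, with 6 of 11 eyes entering at Year 7.5 or later. Footnote a of Table 17.-1 points to the next available visit, the inclusion criteria ask for willingness to attend yearly visits, and the stated expectation is 5 to 7 years. All of this favours earlier entry, although none of it sets a minimum. The moderate pattern gives 4.9 against 4.0%, about 1.2-fold.

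A reader might also infer an open-ended risk period from Protocol 12.4, where data from "follow-up procedures performed up to 6 months after subject exit must be documented". That sentence concerns documentation available to the sponsor on request and does not put such data into the tables. With follow-up planned to Year 10/10A and an Exit Form, the missing cut-off is a gap in wording only.

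Keeping explanted subjects is a deliberate bias-reduction measure (Protocol 8.2), and events after explantation may still be lens-related. That is a reason to show such events separately and not to remove them. Finally, there is no comparator and no test, and the SAP never calls the percent a risk over a fixed period. The percents are thus correct as counts of what was seen; what they lack is a time base.

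**Conclusion.** The point holds on the readable text as an inexpensive improvement that should be made. The adverse event percents and their one-sided limits depend on enrolment timing and cannot be read as risk over a defined period. Planned exposure per eye runs from about 0 to 6.3 years by the windows, or to about 5.3 years for an eye first entering at Year 5.

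The size of the distortion in this trial is unknown. In the illustrations it is about 1.2-fold under moderate spread of entry and reaches about two-fold only under the extreme pattern; the off-lens effect is smaller. All of these rest on assumed hazards, entry patterns and explant fractions. It would go too far to call the percents invalid or the plan's safety conclusion unsound. Redacted parts of both documents may already contain a related analysis.

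**What to change.** In SAP 4.2.2:

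- Keep the percents and their limits, and label them as in-study events with unequal exposure.
- Report total eye-years and subject-years from consent to study exit, and state that cut-off.
- Give ocular events per 100 eye-years and non-ocular events per 100 subject-years, with limits for ocular events that are clustered by subject.
- For the ADE table, add a rate over lens-in-place time, counting a replacement L-series lens as in place, and list post-explantation events separately.
- Optional: show rates by band of years since implantation, because one overall rate still depends somewhat on the entry mix if the hazard changes.

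Editorial: reconcile the stated 5 to 7 years with the entry rule and the visit windows, and say whether it is per eye or per subject.

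Cost: SAP text, a few extra tables and minor programming, with no change to visits. Consent is dated, exit is on the Exit Form, onset day and eye are in the planned listing, in-study explants are reported as serious adverse events with a date, and lens replacement is recorded at entry. Dates of explants before entry must be retrieved from the previous-study data.
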